#### 9.7.2.4 Analysis of the Primary and Secondary Endpoints

The prevalence of major and minor congenital malformations will be calculated using MACDP convention. Major malformations will be analyzed separately from minor malformations, with the primary analysis including only adjudicated major congenital malformations. The total prevalence will be calculated by dividing the number of adjudicated cases of each event (observed in live births, fetal deaths, elective or therapeutic terminations, and at any gestational age) by the total number of pregnancies (excluding spontaneous terminations and ectopic or molar pregnancies). The prevalence at birth will be calculated as number of cases observed in live births and stillbirths divided by the total number of births (stillbirths + live births). Data analysis for major congenital malformations will be based on first trimester exposure to erenumab-aooe.

The prevalence of pregnancy complications, including preeclampsia, pregnancy-induced hypertension, gestational diabetes, placenta previa, and preterm labor, will be summarized by dividing the number of each event by the total number of pregnant women.

The prevalence of spontaneous abortions will be calculated by dividing the number of fetal losses occurring before 20 weeks gestation by the total number of pregnancies.

The prevalence of elective and therapeutic abortion will be estimated similarly as separate outcomes.

Prevalence of preterm birth will be calculated by dividing the number of cases by the total number of births (stillbirths + live births). The prevalence of small-for-gestational-age will be calculated by dividing the number of cases by the total number of live births.

For growth and developmental delays, the prevalence will be calculated as the number of cases divided by the total number of live births.

Prevalence of primary and secondary outcome measures will be presented with 95% CIs for binomial proportion. The analyses summarized in this section will be performed on the erenumab-aooe exposed cohort and the internal comparator cohort consisting of pregnant women with migraine who were not exposed to erenumab-aooe; Characteristics can be matched or stratified in relation to the exposed cohort to control for important covariates such as maternal age (see [Section 9.7.2.5.1](#)).

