#### **9.7.2.6 Sensitivity Analysis**

Sensitivity analyses will be performed on both the erenumab-aooe exposed and internal comparator cohorts if sufficient sample size allows, and include but are not limited to the following:

- A sensitivity analysis of major congenital malformations will include women who have received any prenatal screening, regardless of the findings.
- A sensitivity analysis of major congenital malformations will include women where the result is known, regardless of the findings, prior to enrollment in the registry. Subsequently, a sensitivity analysis of major congenital malformations will include women who received any first trimester prenatal screening before enrollment where the result is known to be negative (see [Table 2](#)).
- Sensitivity analyses will also be conducted to study the effects of the timing of erenumab-aooe exposure before and during pregnancy and cumulative exposure periods on each outcome.
- A sensitivity analysis of major and minor congenital malformations will be performed that analyzes different cut points of exposure to erenumab-aooe, accounting for each trimester of exposure. While the primary cut point will be the date of LMP to the end of the first trimester (14 weeks gestation), additional sensitivity cut points will include: 16 weeks prior to LMP through the end of the first trimester, LMP date to the end of pregnancy, 16 weeks prior to LMP to the end of pregnancy, second trimester exposure only, and third trimester exposure only.
- Spontaneous abortions defined as occurring before 22 weeks gestation will also be examined in a sensitivity analysis to account for global variation in the definition for this outcome.
- A sensitivity analysis will be performed to examine the impact of time-varying exposure on primary and secondary outcomes. A time-varying exposure cox regression model will adjust for fixed covariates such as maternal age, presence of comorbidities, previous history of obstetric complications, and gestational age at exposure as time varying covariate. Details will be provided in the SAP.
- For spontaneous abortion, a sensitivity analysis will be performed based on gestational age at enrollment.

Sensitivity analyses may rely on sufficient sample sizes in order to execute. Full details will be described in the SAP.

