#### 9.7.2.6.1 Subgroup Analysis

Additional subgroups of interest may be explored beyond what is outlined, below. If the difference in subgroups is meaningful, these covariates will be considered for adjustment of confounding in the primary analysis.

- Women in the internal comparator cohort who are migraine treatment naive will be examined separately with respect to the primary and secondary outcomes.
- Both the erenumab-aooe exposed and internal comparator cohorts will be summarized for primary and secondary outcomes both overall and by the subgroups of following parameters, if sufficient sample size allows:
  - Maternal age category
  - Race/ethnicity
  - Smoking status
  - Other classes of migraine therapy used during pregnancy and/or lactation during the infant's first year of life (among live births)
  - Type of migraine: episodic, chronic (with or without aura)
  - Severity of migraine: measured in terms of frequency (occurrence daily, weekly, monthly), time since the date of diagnosis, and presence of aura (ever vs. never), number of prior preventive migraine treatment failures (pre-pregnancy), days of acute migraine treatments each month (pre-pregnancy and by trimester)

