#### 9.7.2.6.2 Stratified Analysis

To examine whether other preventive migraine treatment(s) modifies the association between erenumab-aooe exposure and the primary and secondary outcomes, women with documented exposure to another preventive migraine treatment(s) will be examined for significance in a stratified analysis and with an interaction term in the regression model. If an enrolled registry patient is exposed to any potential or known teratogen either before or after enrollment (including any preventive migraine treatments that are known teratogens), or if there is evidence of exposure to any new/emerging teratogen at the time of final analysis, the registry will be analyzed both including and excluding these women at the time of final analysis, with consideration to the timing of exposure during pregnancy and based on the substances' half-lives (ie, during pregnancy or within 5 half-lives prior to the LMP) ([Appendix G](#)). Stratification will rely on sufficient sample size, with further details in the SAP.

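### The subgroup by other migraine therapy in 9.7.2.6.1 counts use at any time in pregnancy or lactation, so drug use after the outcome or its risk window can define the group; this mainly distorts spontaneous abortion

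*Protocol*

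**What the plan says.** Protocol 9.7.2.6.1 states that both cohorts "will be summarized for primary and secondary outcomes both overall and by the subgroups of following parameters", sample size permitting. One listed parameter is "Other classes of migraine therapy used during pregnancy and/or lactation", the lactation part running through the infant's first year and followed by a bracketed qualifier on live births, with no gestational landmark and no rule for time at risk. The same section says that if subgroup differences are meaningful, "these covariates will be considered for adjustment of confounding in the primary analysis".

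Other sections that bear on it:
- 9.7.2.4 computes spontaneous abortion as a simple proportion, by "dividing the number of fetal losses occurring before 20 weeks gestation by the total number of pregnancies".
- 9.7.2.6 sets the malformation window for erenumab itself: "the primary cut point will be the date of LMP to the end of the first trimester", given there as 14 weeks. Its time-varying Cox model concerns exposure timing and names fixed covariates. It is not applied to the other-therapy groups.
- 9.7.2.1 separately plans a subgroup by migraine medications of special interest at baseline.
- 9.2.7 and 9.2.8 collect medication start and stop dates, beginning 3 months before the last menstrual period (LMP).

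**The concern.** Group membership depends on what happens during follow-up. A pregnancy lost at week 12 had 12 weeks in which to become a user; one delivered near term had about 39. Among women who start in pregnancy, being a user is therefore partly a marker of having stayed pregnant. For malformations, a drug first taken in the third trimester puts a woman in the same group as first-trimester use, although the relevant window has closed.

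Two uses of the result are at stake. The difference between users and non-users can lead to a covariate being considered for the primary analysis. And a reader will compare the erenumab risk ratio between the groups. Either can show a pattern created only by the grouping rule.

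**Working it through.** **Plan's own figure.** The sample size is not affected. 749 live births per group gives 80% power for 3% versus 6%, and 749 / (0.85 × 0.62) = 1421, as stated in 9.5.

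**Assumptions.** The protocol gives no use rates or loss timing, so these are assumed: no drug has any effect; loss risk q = 0.10, spread evenly over weeks 8 to 20; other pregnancies end at week 39; a share u0 already uses other therapy at week 4; the rest start at a constant rate h, so that a proportion U has used by week 39.

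**Formulas.**
- h = −ln[(1 − U)/(1 − u0)] / 35
- Proportion of lost pregnancies classed as users: L = 1 − (1 − u0) × [exp(−4h) − exp(−16h)] / (12h)
- Loss risk in users: qL / [qL + (1 − q)U]
- Loss risk in non-users: q(1 − L) / [q(1 − L) + (1 − q)(1 − U)]

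**Numbers with nobody using at week 4.**
- Comparator, U = 0.30: h = 0.0102, L = 0.0963. Users: 0.00963 / (0.00963 + 0.27) = 3.4%. Non-users: 0.09037 / (0.09037 + 0.63) = 12.5%. Ratio about 0.27.
- Exposed, U = 0.60: h = 0.0262, L = 0.2272. Users: 0.02272 / (0.02272 + 0.54) = 4.0%. Non-users: 0.07728 / (0.07728 + 0.36) = 17.7%.
- Erenumab risk ratio: 17.7/12.5 = 1.41 in non-users and 4.04/3.44 = 1.17 in users. Overall it is 1.00 by construction.

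**Range over use already present at week 4** (30% comparator, 60% exposed eventual use):

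| Share of eventual users already using at week 4 | Comparator loss, users / non-users | User/non-user ratio | Erenumab RR, non-users | Erenumab RR, users |
|---|---|---|---|---|
| none | 3.4% / 12.5% | 0.27 | 1.41 | 1.17 |
| half | 6.8% / 11.3% | 0.60 | 1.26 | 1.03 |
| 80% | 8.7% / 10.5% | 0.83 | 1.12 | 1.00 |

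With the two cohorts' uptake swapped and nobody using at week 4, the ratios are 0.71 (non-users) and 0.85 (users). At 30% versus 40% they are 1.10 and 1.05, or 1.06 and 1.01 if half already use. With equal patterns both are 1.00.

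**Timing alone.** A second set of assumptions has 15% loss over weeks 6 to 20 and 30% ever-use in both cohorts. If exposed users all start in pregnancy and comparator users all use at LMP, the risk ratio is 6.1/15.0 = 0.41 in users and 18.3/15.0 = 1.22 in non-users. If use is fixed at LMP in both cohorts, it is 1.00 in both strata even at 20% versus 50% use.

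**Other outcomes.** Under that second set, across the scenarios with differing frequency or timing, the spurious erenumab risk ratio is 0.89 to 1.06 for preterm birth (assumed 10%, weeks 30 to 37) and 0.85 to 1.09 for malformations (3%, with 30% of cases assumed terminated at weeks 14 to 22).

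**Dilution for malformations.** If a co-medication doubles risk only when taken in the first trimester, and a share f of any-time users took it then, the user group shows 1 + f × (2 − 1). For f of 0.3 to 0.7 that is 1.3 to 1.7 instead of 2. This understates the co-medication's own effect; it is not bias in the erenumab risk ratio.

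**The case against.** The strongest reply has four parts.

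1. **The line is descriptive and conditional.** It applies if numbers allow, and covariates are only to be considered for adjustment. That is so, and it limits the consequence, but the stated window is still unsuitable for early-ending outcomes.

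2. **The live-births qualifier may cover the whole item.** If so, losses and terminations leave this subgroup and only the small effects on live-birth outcomes remain. The phrase can also be read as qualifying only lactation in the infant's first year. The text does not settle it.

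3. **New starts may be few.** Preventives may already be in use at LMP, 7.1 reports improvement or remission in many women as pregnancy advances, and a baseline subgroup is planned in 9.7.2.1. The first point is why the table ranges over prevalent use, and the distortion does shrink. The baseline subgroup is a separate analysis and does not correct this line.

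4. **Section 9.7.2.6.2 should not be charged with the same error.** It says that "women with documented exposure to another preventive migraine treatment(s) will be examined for significance in a stratified analysis and with an interaction term", but gives no window for that grouping and leaves stratification details to the SAP. The half-life window there concerns teratogens. A reader might infer that it too uses any-time exposure; the text does not say so. This objection stands in full.

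**Conclusion.** The point holds for the subgroup line in 9.7.2.6.1, chiefly for spontaneous abortion and other early endings. Once some women start therapy in pregnancy, the user/non-user contrast is distorted: about 0.27 to 0.83 under the stated assumptions, with no drug effect.

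A reader might go further and infer that erenumab risk ratios within these groups must be wrong, or that lost pregnancies rarely count as users. The documents support neither. With equal frequency and timing in the cohorts the risk ratio is 1.00, and women already treated at LMP are users from the start. Bias needs a difference in how often or when other therapy is started. Section 9.9.1.3 makes that plausible, since it expects channelling by severity and treatment history, but gives no rates. Nor is the primary comparison much threatened: 9.7.2.4 leaves spontaneous losses out of the total-prevalence denominator for malformations, and the effect there is small apart from the dilution shown. All sizes rest on assumed loss timing and uptake.

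**What to change.** In 9.7.2.6.1, replace the single any-time grouping with outcome-specific windows:
- **Malformations:** use from LMP, plus the drug's carry-over, to 14 weeks.
- **Spontaneous abortion, termination, stillbirth, preterm birth and complications:** use from 3 months before LMP to enrollment, or time-updated use.
- **Infant growth and development:** the only outcomes grouped by use during lactation.
- State which part of the item the live-births qualifier covers.
- Do not let the any-time user/non-user contrast select adjustment covariates for the primary analysis.

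Apply the same rule when the SAP sets the window for 9.7.2.6.2.

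The cost is wording only, since start and stop dates are already collected. User groups become smaller, and later starters are classed by their earlier status. Enrollment occurs at differing gestational ages, so spontaneous abortion by use at enrollment should be read alongside the analysis by gestational age at enrollment that 9.7.2.6 already plans.

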#### 9.7.2.6.2 Stratified Analysis

To examine whether other preventive migraine treatment(s) modifies the association between erenumab-aooe exposure and the primary and secondary outcomes, women with documented exposure to another preventive migraine treatment(s) will be examined for significance in a stratified analysis and with an interaction term in the regression model. If an enrolled registry patient is exposed to any potential or known teratogen either before or after enrollment (including any preventive migraine treatments that are known teratogens), or if there is evidence of exposure to any new/emerging teratogen at the time of final analysis, the registry will be analyzed both including and excluding these women at the time of final analysis, with consideration to the timing of exposure during pregnancy and based on the substances' half-lives (ie, during pregnancy or within 5 half-lives prior to the LMP) ([Appendix G](#)). Stratification will rely on sufficient sample size, with further details in the SAP.

#### 9.7.2.6.3 Sensitivity Analysis for Residual Confounding and Bias

Not applicable.

#### 9.7.2.6.4 Other Sensitivity Analysis

Not applicable.

### **9.7.3 Analysis of Safety Outcomes**

Interim safety reporting will be conducted every year and will be aligned with the periodic benefit-risk evaluation report (PBRER) reporting schedule. All AE verbatim terms will be recorded and coded using the Medical Dictionary for Regulatory Activities version 21.1 or later. All AEs reported will be analyzed by preferred terms on overall and within erenumab-aooe exposed and internal comparator cohorts.

## **9.8 Quality Control**

### **9.8.1 Study Documentation**

The CC must maintain adequate and accurate records to enable the conduct of the study to be fully documented, including, but not limited to, the protocol, protocol amendments, ICFs, and documentation of IRB and governmental notification. In addition, at the end of the study, the physician will receive the patient data, which will include an audit trail containing a complete record of all changes to data.

Amgen shall ensure that the dataset and statistical programs used for generating the data included in the final study report are kept in electronic format and are available for auditing and inspection.

### **9.8.2 Coordinating Center Audits and Inspections**

CC inspections may be conducted by Amgen or an authorized representative for audit of study data, patients' medical records, and eCRFs.

The CC Investigator will also permit national and local health authorities to inspect facilities and records relevant to this study.

### **9.8.3 Retention of Records**

At the end of the study, the CC Investigator will receive the data related to patients from his or her CC in an electronically readable format (eg, on a compact disc). Data must be kept with the study records. Acknowledgement of receipt of the data is required.

Retention of study documents will be governed by the contractual agreement with the CRO. At study close, data are uploaded from the database, transferred to Amgen and stored in accordance with Amgen SOPs. Statistical programming and outputs are locked in the analysis environment and no updates are permitted; standard programming procedures will apply.

No records may be disposed of without the written approval of Amgen. Written notification should be provided to Amgen prior to transferring any records to another party or moving them to another location.

All supporting functional parties will comply with Amgen procedures regarding archiving and record management.

#### **9.8.4 External Advisors**

A committee of at least 3 qualified, independent teratologists or other appropriate birth defect experts will be used throughout the study for evaluation of congenital malformations and other significant findings. They will be blinded to the patient's exposure status to reduce any potential bias of outcome classification. Other experts in relevant specialties will also be consulted by the Sponsor as deemed necessary by the external advisors.

#### **9.9 Limitations of the Research Methods**

Although all possible measures will be taken to ensure the quality and robustness of the data, there are several limitations inherent to the study design that should be acknowledged.

##### **9.9.1 Internal Validity of Study Design**

###### **9.9.1.1 Misclassifications**

**Assessing Exposures:** Recall of treatment and other potential exposures that could adversely impact the outcome of pregnancy is subject to variability based on the quality of collection by the HCP or the memory of the patient. Where applicable, calendars will be provided to aid the recall of past exposures. Migraines and migraine treatments (apart from other migraine preventive treatments) are generally episodic in nature. However, because erenumab-aooe is a preventive, injectable therapy, patients are more likely to recall timing of erenumab-aooe exposure as opposed to other migraine treatment interventions due to the indication and mode of administration. Exposure histories could be differential based on exposure.

**Assessing the Primary Outcome:** A committee of at least 3 qualified, independent teratologists or other appropriate birth defect experts will be used throughout the study for evaluation of congenital malformations and other significant findings in the erenumab-aooe exposed and internal comparator groups to ensure proper classification of the primary outcome (see [Section 9.8.4](#)). Adjudicators will be blinded to erenumab-aooe exposure status to ensure if any misclassification remained after adjudication would be non-differential.

Misclassification of the primary and secondary outcomes remain possible, even with independent review. Where applicable, information provided by the HCP will override the information provided by the patient, should there be a discrepancy.

#### **9.9.1.2 Information Bias**

Patients who have been informed about a potential adverse pregnancy outcome prior to enrollment in the study may differentially recall their exposures during early pregnancy and may also have changed their exposures after learning of the outcome. This study plans to enroll both women where a fetal diagnosis has been made prior to enrollment in the registry, either positive or negative, for major congenital malformations that are unrelated to genetic or aneuploid disorders), and women with or without prenatal testing prior to enrollment that could determine the status of the fetus) (eg, amniocentesis, genetic testing, nuchal translucency screen, chorionic villus sampling, and late term ultrasound). The differential recall may lead to bias, which will be addressed with the stratification of primary and secondary outcomes by retrospective and prospective status. Additionally, the primary analysis will exclude women who have received first trimester prenatal screening in which either aneuploid disorders or genetic disorders that are known to cause major congenital malformations have been detected.

#### **9.9.1.3 Selection Bias**

Spontaneous abortions most frequently occur in early pregnancy, likely before the pregnancy is recognized. Even if the pregnancy is recognized and confirmed, it is possible that the pregnancy may not be reported to the study if the loss occurred before enrollment into the study. Not capturing all early pregnancy losses will likely lead to an underestimation of the true early pregnancy loss rate. There is no reason to believe that this study will be differentially impacted by this bias so even though the spontaneous early losses may be underestimated, the relative rate compared with the other registries should not be affected.

There is potential for channeling bias by label indication due to the severity of migraine at baseline and patient migraine treatment history. Women with more severe migraines may be indicated for erenumab-aooe use compared with women who have less severe migraine histories. Baseline severity of migraine and prior treatments will be captured to assess the degree of confounding by indication.

#### **9.9.1.4 Confounding**

Covariates collected in both erenumab-aooe exposed and internal comparator cohorts include the following: pregnancy follow-up and frequency of mother and infant

encounters, medical and medication history (including migraine treatment), migraine history, and pregnancy and infant outcomes (see [Appendix F](#)). Careful collection of data elements will be determined based on confounding factors known to be associated with adverse pregnancy outcomes (eg, maternal age, smoking) to examine the distributions between the erenumab-aooe exposed and internal comparator cohorts. The exploration of migraine treatment exposures during pregnancy other than erenumab-aooe, will also be performed by examining specific drugs and/or drug classes. Sensitivity analyses will complement existing primary analysis in controlling for confounding (see [Section 9.7.2.5](#)).

